### **Research Question(s)/Hypothesis(es):**

The purpose of the this study is to determine if patients with back pain who use a device that provides a proprioceptive reminder regarding posture (UPRIGHT device) demonstrate improved pain control and self perception of posture over those who receive a brief instruction on posture and an ergonomic handout.

Hypothesis: There will be no difference in back pain score or self perception of posture between those using the UPRIGHT device and those receiving posture/ergonomic instruction alone.

### **Scientific Abstract:**

Back pain is one of the most common conditions among the adult population (1). There is evidence that individuals with back pain have impaired motor control of trunk muscles and delayed neuromuscular recruitment (2,3). Poor posture has been associated with spinal extensor weakness, back pain, and lower quality of life scores (4). Those who spend prolonged time sitting in poor posture often develop muscular imbalances leading to tight chest muscles and weakness in back muscles. Back pain is commonly treated with flexibility and strengthening and exercises as well and a health education regarding proper posture (5). The purpose of the this study is to determine if patients with back pain who use a device that provides a proprioceptive reminder regarding posture (UPRIGHT device) demonstrate improved pain control and self perception of posture over those who receive a brief instruction on posture and an ergonomic handout.

Hypothesis: There will be no difference in back pain score or self perception of posture between those using the UPRIGHT device and those receiving posture/ergonomic instruction alone. This is a randomized controlled study to determine if patients between the ages of 18-50, with posture related low back pain, who use the UPRIGHT device demonstrate improved pain control and self perception of posture compared to those given standard ergonomic instruction. Subjects will complete a baseline history, physical exam and questionnaire to assess current pain level.

Subjects will be randomized into two groups. One group will receive the UPRIGHT device and a 15 minute tutorial on using the device. Subjects will complete a 4 week training program using the device. The control group will receive a 15 minute instruction on proper posture and an ergonomic handout explaining how to sit and stand with proper posture. At the end of 4 weeks subjects will be contacted via telephone to complete a questionnaire to assess their current pain level, perception of posture, and satisfaction with the device.

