#### **Study Population:**

A total of up to 45 participants will be enrolled into this study with a target accrual of 35 participants treated.

This study consists of two groups:

1. Upright posture device x 4 weeks.
2. Ergonomic instruction (15-20 min) and handout.

The Inclusion Criteria is as follows:

1. Ages 18-50
2. Postural related back pain

The Exclusion Criteria is as follows:

1. A diagnosis of significant scoliosis, herniated/bulging disc, lumbar spondylolysis, radiculitis, facet arthrosis, fibromyalgia, rheumatoid arthritis, seronegative spondyloarthropathy
2. Neurologic deficits on exam
3. Currently in PT

The participants will fall in either one of the following Intervention /exposure groups: Group 1- Upright device training x 4 weeks Group 2- Ergonomic training 30 min, ergonomic handout. The control group will get the upright device if they still have pain.

Randomization will be done by research member not in contact with participant using [www.randomization.com](http://www.randomization.com) and will use 3 blocks of 10 for randomization. At the end of 4 weeks patient will be reassessed with visual analog pain scale, and self perception posture scale. Patients receiving the upright device will have a brief training on the use of the device and proper posture. They will use a training protocol (attached). The control group will have a 15-20 minute instruction on proper posture and an ergonomic handout.

Patients will be identified by a physician at student health and enrolled by the research team. Informed consent will be obtained.

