#### **Study Procedures:**

Subjects with complaints of back pain will be recruited from Columbia University Student Health and from Columbia Doctors Physical Medicine and Rehabilitation practice. Subjects will be consented and randomized to either the UPRIGHT device group or control group. The UPRIGHT group will get a brief training on how to use the device. This will involve downloading the app on subjects phone. We will set

up a separate de-identified gmail account which will be used collect data from the device. They will be instructed on how and where to attach the device to their back. The subject will be asked to sit with proper posture in a chair without leaning against the back rest with both feet flat on the ground. The training is once daily and each day the time increase according to the provided training protocol. The subjects will wear the device once per day for 4 weeks.

The subject needs to use a new adhesive (which will be provided) each time they put the device on. The device will be calibrated to detect changes in posture. A detailed physical exam as well as medical history, family history will be conducted on all participants. Subjects will then be given a 4 week training protocol through the app. The control group will have a 15 minute instruction on proper posture and an ergonomic handout explaining how to sit and stand with proper posture.

At the end of 4 weeks subjects will be contacted via telephone to complete a questionnaire to assess their current pain level, perception of posture, and satisfaction with the device. At the end of 4 weeks participants in the control group will be given an UPRIGHT device if they continue to have pain.

Prior to recruitment we will pilot the use of this device with 5 healthy controls. The purpose of the pilot study is to assess for any difficulties we may encounter with the device and while training with the device.

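### The baseline schedule for self-perception of posture is inconsistent between sections, and the between-group ANOVA names no baseline adjustment

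*Combined protocol and SAP*

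**What the plan says.** **Outcomes.** The hypothesis, in Research Question(s)/Hypothesis(es), covers pain and posture and is a comparison between groups: "There will be no difference in back pain score or self perception of posture between those using the UPRIGHT device" and those given instruction alone.

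**Baseline.** The Scientific Abstract gives: "Subjects will complete a baseline history, physical exam and questionnaire to assess current pain level". Study Procedures gives: "A detailed physical exam as well as medical history, family history will be conducted on all participants". It mentions no questionnaire at that point.

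**Week 4.** The Scientific Abstract describes a "questionnaire to assess their current pain level, perception of posture, and satisfaction with the device", completed by telephone. Study Procedures agrees: "subjects will be contacted via telephone to complete a questionnaire to assess their current pain level, perception of posture". Study Population puts it differently: "At the end of 4 weeks patient will be reassessed with visual analog pain scale, and self perception posture scale".

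**Analysis.** The Statistical Plan uses paired t-tests within subjects, without restricting them to one outcome, and ANOVA between subjects, without naming a covariate or a change score. It plans for 30 participants. Study Population gives a "target accrual of 35 participants treated".

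**The concern.** A paired t-test needs two values of the same measure from each person. For posture, the sections that describe data collection place the scale at week 4 only, while the verb used in Study Population and the paired tests in the Statistical Plan presuppose an earlier value. Staff who work from the Scientific Abstract would collect baseline pain and not baseline posture. A baseline that was not taken cannot be recovered once the intervention has started.

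The loss would be the within-subject test for one of the two named outcomes, any baseline adjustment for it, and any view of whether the arms started alike on it. In a study of about 30 to 35 people, baseline adjustment can matter for precision. The Statistical Plan does not mention adjustment even for pain, for which a baseline is already described.

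**Working it through.** **1. The schedule, section by section**

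| Section | Pain, baseline | Posture, baseline | Pain, week 4 | Posture, week 4 |
|---|---|---|---|---|
| Scientific Abstract | yes | not mentioned | yes | yes |
| Study Procedures | not mentioned | not mentioned | yes | yes |
| Study Population | implied by the verb | implied by the verb | yes, visual analog scale | yes |
| Statistical Plan | implied by paired test | implied by paired test | implied by paired test | implied by paired test |

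No section lists the posture scale at baseline, and two sections imply it. Posture pairs available are 0 if the abstract is followed literally, and up to 30 if the scale is also given at baseline.

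**2. Related gaps in the pairs**

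- The baseline pain instrument is not named. The week-4 instrument is a visual analog scale in Study Population, but the week-4 contact is by telephone, and no section says how a visual scale is answered that way.
- Order is not stated outright. The abstract describes baseline before randomisation. Study Procedures says "Subjects will be consented and randomized to either the UPRIGHT device group or control group" and mentions the exam later.

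**3. What a baseline could add to the between-group comparison (illustration)**

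The plan has no power calculation, so there is no figure to reproduce.

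Input from the documents: 30 participants (Statistical Plan), which matches 3 blocks × 10 = 30 (Study Population).

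Assumptions: 1:1 allocation (15 per arm), no dropout, two-sided 5%, 80% power, and a baseline-to-week-4 correlation r of 0.3, 0.5 or 0.7.

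Method: two-sample noncentral t, with noncentrality (d/s) ÷ √(1/n₁ + 1/n₂). Here d is the difference in units of the week-4 SD and s is the relative residual SD.

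- Week-4 values only: s = 1, df = 30 − 2 = 28.
- ANCOVA: s = √(1 − r²), df = 27. The residual variance 1 − r² is 0.91, 0.75 or 0.51.
- Change score: s = √(2(1 − r)), df = 28. The variance 2(1 − r) is 1.4, 1.0 or 0.6.

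Detectable difference with 15 + 15, in SD:

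| Analysis | r = 0.3 | r = 0.5 | r = 0.7 |
|---|---|---|---|
| Week-4 values only | 1.06 | 1.06 | 1.06 |
| ANCOVA | 1.01 | 0.92 | 0.76 |
| Change score | 1.25 | 1.06 | 0.82 |

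With 35 treated (18 + 17), week-4 values alone detect 0.98 SD and ANCOVA detects 0.93, 0.85 or 0.70 SD.

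Power at an assumed true difference of 0.8 SD, with 15 + 15, is 56% on week-4 values. ANCOVA gives 60%, 68% or 84%, and change scores give 43%, 56% or 78%.

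A collected baseline that the analysis ignores leaves the figure at 1.06 SD. A baseline used through change scores is worse than or equal to week-4 values alone up to r = 0.5. Only the adjusted analysis improves on week-4 values at all three correlations.

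**The case against.** The strongest reply is that this is loose wording and not a missing measurement. The abstract's clause states what the baseline questionnaire is for and need not be a full list. Study Procedures omits a baseline questionnaire even for pain, so silence in these short sections is weak evidence about what will be collected. Study Population and the paired tests both point to a posture baseline. This stands. A reader might infer that the trial plans no posture baseline, and the documents do not support that.

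Second, the hypothesis is between groups. A paired test within an arm does not compare the device with instruction, so losing it leaves the hypothesis test intact. This also stands. A reader might infer that the posture comparison would be invalid without a baseline. It would not be, because randomisation supports the comparison of week-4 values.

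Third, the precision figures do not measure the cost of the schedule gap under the plan as written, because the plan's ANOVA names no baseline. This stands too. The figures show what ANCOVA would add, at correlations the documents do not give.

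Fourth, the order of assessments is less open than it looks. A neurologic deficit found on exam is an exclusion criterion, so some exam must come before enrolment, and the abstract also puts baseline first. That is fair for the exam, but it does not fix when a questionnaire is given. The timing, telephone and instrument points are mostly missing detail and add little weight.

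The inconsistency itself remains: the analysis needs a value that no description of data collection schedules.

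**Conclusion.** The point holds as an inconsistency in the baseline schedule for one of two named outcomes, together with a between-group method that does not use baseline. A posture baseline was probably intended. If the abstract is followed literally, the posture paired test has 0 pairs and baseline adjustment for posture is impossible, while the randomised week-4 comparison remains valid.

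The reason to act is that an uncollected baseline cannot be recovered. The possible gain in precision is a second and separate reason. At 15 per arm it runs from slight (1.06 to 1.01 SD at r = 0.3) to substantial (1.06 to 0.76 SD at r = 0.7), and it depends on changing the analysis. It rests on the assumed correlations, equal allocation, no dropout, 80% power and two-sided 5%.

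This should be corrected but does not undermine the trial. Confidence is medium, because the wording leaves the intent open.

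**What to change.** 1. **Schedule.** In the Scientific Abstract and Study Procedures, state that every participant completes the same self-perception of posture scale and the same pain measure before randomisation and again at 4 weeks. Name the pain measure and choose a form that can be answered by telephone, for example a spoken 0–10 rating. Align Study Population with this. If no posture baseline is wanted, limit the paired t-test to pain and say that posture is compared at week 4 only.

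2. **Analysis.** In the Statistical Plan, replace the unadjusted between-group ANOVA with ANCOVA of the week-4 value adjusted for the baseline of the same outcome, separately for pain and posture. For pain this uses a baseline already described. If no posture baseline is collected, ANCOVA applies to pain only.

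**Cost.** A few minutes per participant at baseline, wording changes in three sections, one sentence in the Statistical Plan, and one degree of freedom per model. If a spoken rating replaces the visual analog scale, results are less directly comparable with studies that used that scale. Limiting the paired test to pain adds no participant burden but gives up the posture pairs and the adjustment for posture.

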#### **Study Population:**

A total of up to 45 participants will be enrolled into this study with a target accrual of 35 participants treated.

This study consists of two groups:

1. Upright posture device x 4 weeks.
2. Ergonomic instruction (15-20 min) and handout.

The Inclusion Criteria is as follows:

1. Ages 18-50
2. Postural related back pain

The Exclusion Criteria is as follows:

1. A diagnosis of significant scoliosis, herniated/bulging disc, lumbar spondylolysis, radiculitis, facet arthrosis, fibromyalgia, rheumatoid arthritis, seronegative spondyloarthropathy
2. Neurologic deficits on exam
3. Currently in PT

The participants will fall in either one of the following Intervention /exposure groups: Group 1- Upright device training x 4 weeks Group 2- Ergonomic training 30 min, ergonomic handout. The control group will get the upright device if they still have pain.

Randomization will be done by research member not in contact with participant using [www.randomization.com](http://www.randomization.com) and will use 3 blocks of 10 for randomization. At the end of 4 weeks patient will be reassessed with visual analog pain scale, and self perception posture scale. Patients receiving the upright device will have a brief training on the use of the device and proper posture. They will use a training protocol (attached). The control group will have a 15-20 minute instruction on proper posture and an ergonomic handout.

Patients will be identified by a physician at student health and enrolled by the research team. Informed consent will be obtained.

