**Recruitment:**

Patients will be identified by a physician at student health or by a Columbia Doctors PM&R physician who will first introduce the study to the patients and enrolled by the research team. Informed consent will be obtained. Subjects who presents to the Columbia Health Clinic or Columbia Doctors Rehabilitation Medicine with complaints of back pain who meet the criteria will be asked to participate in our study. Information about the study will be provided and if they choose to participate they will be consented by our research coordinator. They will then be scheduled for study assessments. This study is completely voluntary. None of residents, students, fellows or employees within our Rehabilitation Department will be asked to participate in this study. Recruitment flyers will also be placed in the Department of Rehab at CUMC as well as displayed at student health at Columbia University.

An electronic flyer (attached) will be sent to the graduate school of arts and sciences communication department for them to attach to their monthly newsletter sent to the graduate students on our behalf. The communication department will not give us their list serve at any time. Graduate students are added to this list serve when registered for graduate classes at Columbia University and the communications department is the sole owner of this list. An individual who wants to participate in the study will contact [name] directly and no one from the communication department will ever see this information.

[name], an employee of Upright, will send out the attached email (Upright\_email script) to individuals who have purchased an Upright device in the past on our behalf. We will never have access to these individuals' contact information or listserve. When someone purchases an Upright device they are added onto their mailing listserve and agree to receive emails from Upright. [name] and Upright will be sending the email referencing our study and provide our contact information. An individual who wants to participate in the study will contact [name] directly and no one from Upright will ever see this information.

**Title:** Upright Back Posture Device Study (AAAR4123)

**NCT:** NCT03769246

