**Statistical Plan:**

No power analysis will be done, as only one other study has been published using this device. We'll be using 30 participants, as this study had 30 subjects participating in study.

For within subjects, data will be analyzed using paired T-test analysis. For between subjects data will be analyzed using ANOVA. Currently there are no similar studies to determine the sample size, we plan to analyze the outcomes.

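### The fixed block size of 10, with arms that cannot be masked and no stated concealment of block size or past assignments from enrolling staff, makes some assignments predictable

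*Combined protocol and SAP*

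**What the plan says.** The randomization rule stands under Study Population. The list comes from a public web generator, and the trial "will use 3 blocks of 10 for randomization". The same sentence contains a safeguard: "Randomization will be done by research member not in contact with participant". Three blocks of 10 make 30 positions, which agrees with the Statistical Plan ("We'll be using 30 participants, as this study had 30 subjects participating in study").

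There are two arms ("Subjects will be randomized into two groups", Scientific Abstract). The allocation ratio is not stated.

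On enrolment, Study Population says "Patients will be identified by a physician at student health and enrolled by the research team", and Recruitment says of those approached that "if they choose to participate they will be consented by our research coordinator". Study Procedures puts consent before randomization. It has the team set up the account that collects device data, and does not name who trains participants. No blinding is described. The document does not say how an assignment is released, or whether the coordinator is kept from knowing the block size and the assignments already made.

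**The concern.** A list holder who never meets participants keeps the list out of sight. That does not stop colleagues from counting the assignments already issued. One arm leaves with a device and the other with a handout, so issued assignments are open to whoever delivers them. With a constant block size, once one arm has its share of a block, the rest of that block is determined. Before that point, the arm that is behind is the better guess.

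Foreknowledge matters only if enrolment can respond to it, and here it can to some extent. Back pain related to posture is an inclusion criterion without an operational definition, and a person can be approached sooner, later or not at all. Pain and posture perception are both self-reported. The planned paired t-test and ANOVA cannot remove selection on prognosis that nobody measured.

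**Working it through.** **Inputs.** From the document: block size 10, three blocks, two arms, 30 participants. Assumed: 1:1 allocation (5 and 5 per block, 15 per arm), completed blocks, and an observer who knows the block size and every earlier assignment in order. The document states no figure for predictability, so there is none to reproduce. The only check on its own numbers is 3 × 10 = 30.

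**Assignments certain in advance.** For a balanced block of 2m, the expected number of positions left once one arm is used up is 2m/(m+1).
- Block of 10, m = 5: 10/6 = 1.67. Over three blocks: 3 × 1.67 = 5.0 of 30. Listing all 252 orderings of a 5:5 block gives the same value.
- Spread over three blocks: at least 3 (the last of each block), exactly 3 with probability 0.17, and 3 to 7 with probability 0.93.
- Other ratios: 6:4 gives 5.3 of 30, and 7:3 gives 6.4.
- Less knowledge: 2.0 of 30 if the latest assignment is not yet known, and 0.7 if the latest two are not.

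**Guess rate.** Always guessing the arm that is behind gives an expected number correct per block of m + 2^(2m−1)/C(2m, m) − 0.5.
- m = 5: 5 + 512/252 − 0.5 = 6.53 of 10, or 65.3%. That is 19.6 of 30, against 15 by chance.
- If the latest assignment is unknown: about 60%.

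**Illustrative bias.** Suppose enrolment decisions shift the expected outcome by d SD in the direction of the guessed arm. With guess rate p, each arm mean moves by d(2p − 1) in opposite directions, so the bias in the difference is 2d(2p − 1).
- d = 0.25 (assumption), p = 0.653: 2 × 0.25 × 0.306 = 0.15 SD.
- Range for d from 0.1 to 0.5: 0.06 to 0.31 SD.
- For scale, the standard error of the difference at 15 per arm is √(2/15) = 0.37 SD.

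**Alternatives at 30 participants, observer knowing every earlier assignment.**

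| List | Certain of 30 | Guess rate | Bias at d = 0.25 |
|---|---|---|---|
| Three blocks of 10, size known | 5.0 | 65% | 0.15 SD |
| One balanced list, 15:15 total known | 30/16 = 1.9 | 17.96/30 = 60% | 2 × 0.25 × 0.197 = 0.10 SD |
| Blocks of 8, 10 and 12, sizes known but not their order | 2.3 (simulation) | near 65% | 0.15 SD |

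Varying the block size reduces certainty. It leaves the running-count guess, and so the illustrative bias, where it was.

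**The case against.** The strongest reply is that 5 of 30 describes an observer whom the document does not show to exist. The coordinator takes consent, but nothing says that this person trains participants, sees every assignment or knows the order across two recruiting sites. The shared account work shows visibility at team level only. A reader might therefore infer that five assignments will be known before consent, or that the person who consents also delivers the device. The document supports neither. Missing just the latest assignment brings the 5 down to 2. This part of the objection stands, and it is why the figure is given as an upper bound.

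Discretion is also limited. In the clinics a physician identifies the patient and introduces the study, and consent comes before randomization. Both help. But volunteers reached through flyers, the newsletter or the manufacturer's e-mail may contact the team directly, and the order of consent and randomization does not prevent prediction from earlier assignments.

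A reader might further infer that one or two steered enrolments would decide the trial. At the assumed 0.25 SD, one person moves an arm mean by 0.25/15 = 0.017 SD, so that inference fails. Nor is 10 a poor choice among fixed sizes: known blocks of 6 or 4 would make 7.5 or 10.0 of 30 certain.

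What the objection does not remove is the gap in the text. The block size is fixed in the protocol, the arms are visible, and no concealment from enrolling staff is described beyond who does the randomization.

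**Conclusion.** The point holds as a cheap improvement to the design. It does not show that bias will occur. Under 1:1 allocation and full knowledge of block size and past assignments, up to about 5 of 30 assignments on average are deducible and the next arm can be guessed 65% of the time. With the latest assignment unknown, these become 2 and about 60%. The 0.15 SD bias rests on an assumed 0.25 SD shift and is well below the standard error of 0.37 SD, but unlike sampling error it would run in one direction and could not be seen in the data. One balanced list lowers all three quantities. Varying block sizes lower only the number of certain assignments.

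**What to change.** 1. Replace the three blocks of 10 with one balanced list covering the planned number.
2. If blocks are kept, vary their sizes (for example 8, 10 and 12 in random order) and let only the list holder know them. State that this reduces certain assignments, to about 2.3 of 30 even if the three sizes leak, but leaves the running-count guess near 65%. Do not use very small blocks.
3. In either case, add a sentence that the list holder releases each assignment only after consent and confirmed eligibility are logged, and that the list details are kept from enrolling staff.
4. Reconcile the list length with Study Population, which says "A total of up to 45 participants will be enrolled into this study with a target accrual of 35 participants treated". A list of 30 covers neither number. The 35 may be 30 plus the five pilot volunteers in Study Procedures, but the document does not say so. For 1:1 allocation the length must be even. A list of 36 or 46 would make 36/19 or 46/24, about 1.9, assignments certain if used in full.
5. If enrolment has begun, apply the change to assignments not yet issued.

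The cost is a newly generated list and a few sentences, with no extra staff, patients or procedures. The downside is some possible imbalance between arms if enrolment stops before the list is used up.

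### Does a week-4 visual analog pain score gathered around a telephone contact, with the baseline mode unstated, undermine the pain analysis?

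*Combined protocol and SAP*

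**What the plan says.** Three sections bear on how pain is measured.

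- **Week-4 instrument.** Study Population: "At the end of 4 weeks patient will be reassessed with visual analog pain scale, and self perception posture scale".
- **Week-4 route.** Study Procedures: "At the end of 4 weeks subjects will be contacted via telephone to complete a questionnaire to assess their current pain level". The Scientific Abstract says the same. Neither section names the visual analog scale.
- **Baseline.** Scientific Abstract: "Subjects will complete a baseline history, physical exam and questionnaire to assess current pain level". No instrument or mode is given. Study Procedures adds "A detailed physical exam as well as medical history, family history will be conducted on all participants", and Recruitment says of consenting subjects "They will then be scheduled for study assessments". Both suggest a visit at baseline, but neither says how pain is scored there.

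The Statistical Plan has two analyses: "For within subjects, data will be analyzed using paired T-test analysis" and "For between subjects data will be analyzed using ANOVA". It gives no SD, no significance level and no power calculation.

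**The concern.** A visual analog scale is a line that the participant marks, and a telephone call offers no line. Read literally, the week-4 score might be a spoken number, which is a different measure from the one Study Population names. If baseline pain was marked on a form at a visit and week-4 pain was spoken, the two scores would differ in mode.

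That would matter for the paired t-test. The mean change within an arm would equal the true change plus the whole of any mode shift, and the test cannot separate the two. The direction of such a shift is unknown, so improvement could be overstated or hidden. Pain is one of the two outcomes in the research question, so a reader should be able to tell what was measured.

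**Working it through.** **Reading the sections together.** Study Population names the scale, and the Abstract and Study Procedures name the route of contact. These answer different questions. The telephone text says that subjects are contacted in order to complete a questionnaire. It does not say that answers are spoken, so a form sent ahead or by link, with the call as a prompt, satisfies all three sections.

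The Abstract uses almost the same description at both times: "Subjects will complete a baseline history, physical exam and questionnaire to assess current pain level" at baseline, and "subjects will be contacted via telephone to complete a questionnaire to assess their current pain level" at week 4. Study Population speaks of patients being reassessed. The ordinary reading is one pain questionnaire, containing the visual analog scale, used twice. The questionnaire is not in the text available for review.

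**What a mode effect would do.** The plan has no figure of its own to reproduce here. The only arithmetic it offers is 3 blocks × 10 = 30, which agrees with the 30 participants in the Statistical Plan. The rest is illustration.

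Assumptions: two-sided alpha 0.05; equal allocation, so n = 30 / 2 = 15 per arm; no true change; a mode shift of d SD of the change score.

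Under these, the paired t statistic is noncentral t with 14 degrees of freedom and noncentrality d√15. The critical value is 2.145.

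| d | d√15 | Rejects in direction of shift | Rejects in opposite direction | Total |
|---|---|---|---|---|
| 0 | 0 | 2.5% | 2.5% | 5.0% |
| 0.05 | 0.194 | 3.8% | 1.6% | 5.4% |
| 0.1 | 0.387 | 5.5% | 1.0% | 6.5% |
| 0.2 | 0.775 | 10.8% | 0.4% | 11.2% |
| 0.3 | 1.162 | 19.0% | 0.1% | 19.2% |
| 0.5 | 1.936 | 43.8% | 0.0% | 43.8% |

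The total runs from about 5% to 44% according to the shift chosen, and nothing in the documents favours one row over another. The table describes the assumption, not this trial.

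**The between-arm comparison.** Let the shift be s in both arms. The difference in mean change is (Δ₁ + s) − (Δ₂ + s) = Δ₁ − Δ₂, so s cancels. It cancels in the same way if week-4 values are compared. In 200,000 simulated trials with 15 per arm and a two-sample t-test (equivalent to a two-group ANOVA), the false-positive rate was 4.98% with no shift, 5.05% at 0.1 SD and 4.97% at 0.2 SD. The same week-4 contact is planned for both arms, so an equal shift is the natural expectation, although it is not guaranteed.

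**The case for a change.** The strongest case for a change is that two teams could follow this text and collect different things, one a marked line and the other a spoken number. That does not depend on any argument about bias. The paired t-test is a planned analysis and needs the same measure at both times. The documents mark the training protocol, flyer and email script as attached but never mention an attached questionnaire, so one cannot assume that a form settles the matter. Naming one instrument and one mode would take a few words and no extra visits.

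Part of this stands. The text does not say how the scale is completed around the call, and if answers were spoken, the result should be reported as a spoken rating and not as a visual analog scale. But that is an absent detail. No stated rule produces a wrong result.

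The more specific remedies each have a price. A self-completed electronic scale risks non-response at week 4 in a trial of about 30, and missing data would hurt the randomised comparison, which is otherwise untouched. A spoken 0–10 rating replaces the outcome that the plan names and gives up direct comparability with visual analog results. Choosing between them is a trade-off that the documents do not force.

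**Conclusion.** No change to the plan follows. The sections are compatible, and their wording favours one pain instrument at both times. A bias would need three things that the documents do not state: an in-person baseline score, spoken answers at week 4, and a shift between the two modes.

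If all three held, the harm would fall on the within-arm paired test: a false-positive rate of 6.5% to 11.2% instead of 5% for an assumed shift of 0.1 to 0.2 SD, with 15 per arm and no true change. The actual size and direction cannot be known from the documents. That test has no comparator in any case, so matching the modes would not turn it into evidence of a device effect. The between-arm comparison keeps its error rate as long as the shift is equal in both arms.

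The study team can fill the gap in the ordinary course of work by using the same form in the same way at both times and describing the measure accurately when reporting it.
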